Results are better in paroxysmal patients, than for persistent AF, also for CBA. [13] Nevertheless, persistent patients with normal left atrial dimensions made up an important proportion of our group. [15] Differentiation between paroxysmal and short term persistent becomes almost impossible from a clinical point of view, as patients get early cardioversion, before they are spontaneously reverted to sinus rhythm. [16] Real longstanding persistent patients, however were excluded from our and all previous trials, as were patients with very large atria. Larger atria have more recurrences than smaller atria. Successful ablation results in a smaller left atrial volume, which was shown in several studies with RF, also for paroxysmal patients. [17] This volume reduction is antiarrhythmic as well.

It has been hypothesized that early therapy prevents further progression of the disease. [16] This has never been proven for catheter ablation, while some pilot trials were promising. [18] Reduction of left atrial volume can be used as a substitute for antiarrhythmic efficacy and for less disease progression.

RATIONALE

Limited data indicate that ablation is better than AAD therapy. The 9 small randomized clinical trials as recently summarized by health care authorities with a correct methodology only included 971 patients, and only studied radiofrequency ablation. [19] However, there was substantial heterogeneity, with a majority of paroxysmal patients, but some had mixed groups. Endpoints in these trials were not always clear and variable as well. Side effects of ablation were somewhat neglected. Stop-AF only addressed paroxysmal patients (but included 22% cardioverted patients) and has recently been published. [14] This opens the perspective to organize a prospective trial comparing the efficacy and safety of CBA to standardized medication for treatment of paroxysmal AF and early onset persistent AF without structural heart disease. As elsewhere a trial is launched for first onset paroxysmal AF, we would like to focus in this protocol *on early onset persistent AF without structural heart disease*. The value of CBA in these patients has never been studied; the endpoints for persistent patients are much easier than for paroxysmal patients. Reduction in LA size can be compared versus patients on drug therapy and versus failing patients.

HYPOTHESIS

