1. The results of CBA in early onset persistent AF are better compared to standard medical therapy with as endpoint maintenance of sinus rhythm after 1 year and an improved QOL in the ablation group.
2. Successful CBA results in reduction of the LA volume.

INCLUSION/EXCLUSION CRITERIA

The total AF history is regarded for previous episodes, paroxysmal or persistent. ~~should be shorter than 24 months~~. Symptomatic patients can be included if they have had at

least 2 episodes in their total history, of which one within the last year. One episode in the entire history should have lasted more than 7 days **48 h**, requiring electrical or pharmacological cardioversion or stopped spontaneously after more than 7 days. The duration of this episode should be shorter than 1 year. If one episode is paroxysmal it should have been lasting minimal 30 sec.

All patients eligible for the study will sign informed consent, have an echocardiogram prior to inclusion to exclude severe left ventricular dysfunction, to rule out significant valve abnormalities, left ventricular hypertrophy and to assess the left atrial (LA) volume and diameter.

Prior to randomization, and after inclusion it is suggested to the local investigators to perform an MRI-scan or CT scan of the LA and pulmonary veins (in both branches of the study) in eligible patients to assess the anatomy and the left atrial volume. The results should not influence the strategy of treatment.

Inclusion criteria

- > 21 years and legally capable
- history of 2 symptomatic AF episodes more than 30 sec .
- At least one AF episode within the last year
- One episode cardioverted after more than 7 days or spontaneously terminated after more than 7 days; this episode should have been shorter than one year
- Eligible for at least one first step drug therapy (sotalol, propafenone, or flecainide) **and/or** for amiodarone

- Left ventricular ejection fraction estimated > 45%
- LA diameter < 50 mm (parasternal short axis) **and/or** LA volume less than 100 ml (apical view, Area Length method)
- No previous CVA or TIA (the latter with documented deficit on CT scan)
- ~~CHADS2VASC ≤ XXXX~~
- Failed AAD strategy, or untreated with AAD
- No use of Amiodarone in the previous 6 weeks (except IV or oral for 7 days)
- Informed consent

Exclusion criteria

- Age **> = 80** yrs
- CHF
- Ischemic heart disease as known in the history
- (Severe) Left ventricular hypertrophy as shown on echo (IVSd or PWd > 14 mm)

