- Uncontrolled Hyperthyroidism
- Congenital heart disease
- HCM, ARVC, channelopathies
- Contra-indications to AAD
- Long QT syndrome

- Received already adequately dosed all level 1 drugs (sotalol, propafenone, and flecainide) and >6 weeks amiodarone
- Pure (typical) atrial flutter as documented on one occasion

INVESTIGATION DESIGN

Type

Randomized study design. Experienced centres/operators with a load of > 50 cryoablations/year.

Randomization

1:1 at the time of inclusion

SAMPLE SIZE

The maximal expected 1 year success on AAD is 50% and minimal expected success of CBA is 72%. [3,14,15,20,21,22] With a power of 0.8 and a significance of 0,05, approximately 76 patients should be included in each arm. A total number of 167 patients need to be included in the study when anticipating that 10% of the patients will not be followed as required.

INTERVENTIONS

Run-in period (from month -1 till month 0)

Holter recording in the month after inclusion, preferably directly after inclusion to avoid extra visits.

MRI or CT scan to measure LA volume and PV sizes and anatomy is encouraged

(optional – if done it should be done in both branches)

Ablation arm (at month 0):

The ablation approach should be as standardised as possible, and will be discussed at the investigators meeting

After venous punctures, 5000 IE of heparin is administered and after the transseptal puncture (TSP) this is repeated. Hereafter, heparin infusion is started with a target ACT of at least 275-300 s. A multipolar catheter will be introduced into the coronary sinus. Single TSP will be performed (guided by X-ray and intracardiac echocardiography or transoesophageal echocardiography). The 12 Fr steerable sheath is introduced into the LA, and the second generation (large) cryoballoon with the Achieve catheter is introduced. Before ablation is started, the veins are checked for entrance and exit block. If there is conduction a balloon application is given during 300 s. The occlusion grade, maximal freezing temperature and time to isolation are noted. Every vein with potentials is ablated at least twice with at least one grade IV occlusion, except when PNP occurs at the right upper PV. If not isolated, a third application can be given. If after the third application the vein is still not occluded it is up to the physician to decide to do another balloon application or to use a freezer catheter.

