If isolated, the veins are checked after 30 minutes again for entrance and exit block. The left sided veins are ablated while pacing from the distal CS electrodes and when ablating the right sided veins the phrenic nerve is stimulated to prevent phrenic nerve palsy (PNP). When all veins are isolated AF induction is preformed, 5 s of pacing with CL 200 ms from the distal CS, LA roof (twice) en the HRA. Procedure times , X-ray times, and the radiation dose (mGy) are noted.

Ablation should be scheduled 4 weeks after cardioversion/inclusion. All patients should

be anticoagulated for at least 4 weeks prior to ablation. Antiarrhythmic drugs are maintained after cardioversion. One day before or the day of ablation a TEE will be made to exclude a LAA thrombus. Anticoagulation can be continued if this is the protocol of the participating centre, and the local protocol per ablation should be followed.

Proposed first level:

A: propafenone 300 mg BID / 150 mg QID if < 70 years and > 70 kg

propafenone 150 mg TID if ≥ 70 years or < 70 kg

B: sotalol 120 mg BID if men ≤ 70 years, cr ≤ 1,5mg/130 µmol, > 70kg;

80 mg TID if men ≥ 70 years, cr > 1,5mg/130 µmol, < 70kg;

if women ≤ 70 years; cr ≤ 1,2/110 µmol

80 mg once if women > 70 years or cr > 1,2 mg/110 µmol

C: Flecainide : Apocard Retard 100 mg/day as startdosis 4 to 5 days

Further 200 mg/day

Tambocor 100 mg BID if preferred

Proposed second level:

Amiodarone: loading 14 days with 600 mg/day

One week 400 mg/day

Maintenance 200 mg/day

Drug arm:

Anticoagulation should be continued per protocol (4 weeks) after the cardioversion. If the CHADS2VASC is \leq 2, anticoagulation is left at the discretion of the physician. A first level antiarrhythmic drug regimen is started at the month -1, time of the inclusion and

an adequate dosage is prescribed. If the patients' condition requires so, a reduced dosage can be used during the first (5-7) days.

If at month 0, at the first clinical visit, the drug therapy does not look sufficient, another

Level 1 treatment can be used. This can be repeated if the clinical condition requests so.

The second slevel antiarrhythmic drug therapy is only allowed after failure of at least one level 1 drug. As this is amiodarone, its final efficacy can only be judged 6 months after its initiation.

FOLLOW UP : see flow charts Is in agreement with proposal in ref 23.

- 24 hour Holter:

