 - after inclusion (month -1) and repeated at months 3 .This will be done with the study Holter without necessarily influencing the therapy (so called blanking period)
- 48 hour Holter: with a clinical device
 - at the end of 6 months .
- 7 days Holter: with a clinical device
 - at the end of 12 months .
- Clinical visits :

should be performed by the study nurses/supervised by the investigators

- At months 3, 6, and 12 months after ablation
- Additionally at month 0 for the drug arm, while the ablation group is admitted
- Office ECG ;
 - ° at month 3, 6 and 12
- Drug management:
 - AAD: After 3 months stop AAD in the ablation arm in those patients free of AF episodes.
 - OAC: After 6 months consider stopping oral anticoagulation, or replacing them with antithrombotic medication in patients free of AF episodes if the scores allow so.
- Echocardiogram:
 - At month 12 a new echocardiogram is obtained to assess the LA volume and diameter.
- QOL with disease specific questionnaire (AFQOL 18)
 - At baseline and at month 12
- Blood samples
 - At baseline and at months 6 and 12
 - Thyroid tests (TSH), liver function (AP, SGOT, SGPT), creatinine

- Drug diary
 - At baseline, at month 0 and at months 6 and 12 for all patients in both arms
- Cost calculation: data should be prospectively collected in CRF at the time of scheduled and unscheduled visits, based on costs as foreseen in the reimbursement of the RIZIV/INAMI and additional drug costs.

CROSS OVER

Is allowed after 6 months. This implies that at 12 months we will be able to do not only ITT but also OTA.

SERIOUS ADVERSE EVENTS

SAE's are expected to happen in 7% in the ablation arm, and at a rate of 12-15% in the drug arm, because of side effects and 3% because of proarrhythmia (20).

ENDPOINTS

Primary endpoints

- Sinus rhythm at clinical visit at 1 year after the ablation, or with AAD
- Freedom of AF with all measurements

Secondary endpoints

- Reduction of LA volume in successfully treated patients
- Number of cardioversions
- Percentage of patients on AAD after 6 and 12 months

- Vascular complications
- Stroke, TIA
- SAE in both groups
- Number of cross-overs (with OTA)

[figure not shown]

Figure 1. AAD : antiarrhythmic drugs; LA: left atrial; QOL: quality of life; R: randomization

STUDY ORGANISATION

Steering committee : [name], [name], [name], [name]

DMSB : [name], [name], [name]

One central study coordinator (University Hospital Ghent) – [name]

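### The first primary endpoint scores one rhythm reading at 1 year, so a patient who relapsed and was cardioverted or re-ablated before the visit counts as a success; the second primary endpoint only partly closes this gap

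*Protocol*

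**What the plan says.** All references are to the Protocol.

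- **Endpoints, primary.** Two are listed. The first is "Sinus rhythm at clinical visit at 1 year after the ablation, or with AAD". The second is "Freedom of AF with all measurements". The text does not say whether both must be met, either suffices, or each is tested separately.
- **Endpoints, secondary.** The list includes "Number of cardioversions". Cardioversion is counted there but plays no part in the wording of either primary.
- **Hypothesis, item 1.** The comparison is framed "with as endpoint maintenance of sinus rhythm after 1 year".
- **Interventions.** Cardioversion appears around inclusion and ablation ("Ablation should be scheduled 4 weeks after cardioversion/inclusion") and in the anticoagulation instructions. There is no rule for cardioversion in follow-up. Repeat ablation is neither excluded nor scored, although the Background says it improves radiofrequency results.
- **Follow up.** Rhythm is recorded by 24-hour Holter after inclusion and at month 3 (called the blanking period), 48-hour Holter at month 6 and 7-day Holter at month 12. Office ECGs are at months 3, 6 and 12.
- **Sample size.** "The maximal expected 1 year success on AAD is 50% and minimal expected success of CBA is 72" (per cent). With power 0.8 and significance 0.05 this gives about 76 per arm. The rates are called 1-year success and are not tied to either primary.

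**The concern.** Maintaining sinus rhythm and being in sinus rhythm on one day are different outcomes. In persistent AF the difference matters, because cardioversion itself produces the result that the first primary scores. A patient who relapses at month 9, is cardioverted and is in sinus rhythm at month 12 has not maintained sinus rhythm on the assigned treatment, but is a success on that endpoint as worded. The same holds for a second ablation in the ablation arm.

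Two consequences follow. If rescue is used equally, some failures in both arms become successes and the difference shrinks. If it is used unequally, the arm with more rescue gains. The Protocol describes no blinding, and a catheter procedure against drugs makes the arm evident to whoever decides on rescue and its timing, so unequal use is possible.

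This is separate from cross-over: these patients stay on their assigned strategy.

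**Working it through.** **Step 1. Does the second primary catch the rescued patient?** Take a patient with AF at month 8 who is cardioverted the same month and remains in sinus rhythm.

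- First primary: success, since only the 1-year visit counts.
- Second primary, if unscheduled ECGs or the cardioversion count as measurements: failure.
- Second primary, if only scheduled recordings count: success. The 48-hour Holter at month 6 precedes the relapse, the 7-day Holter at month 12 follows the rescue, and nothing is scheduled between them.

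The text does not say which reading applies, so the second primary narrows the gap without closing it.

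**Step 2. Reproduce the plan's figure.** Inputs from Sample size: p_D = 0.50 (drugs), p_A = 0.72 (ablation), power 0.80, alpha 0.05 (sidedness not stated; taken as two-sided), allocation 1:1. Pooled-variance test without continuity correction at n = 76 per arm:

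- mean rate = (0.50 + 0.72)/2 = 0.61
- SE under the null = √(0.61 × 0.39 × 2/76) = 0.0791
- SE under the alternative = √((0.50 × 0.50 + 0.72 × 0.28)/76) = 0.0771
- power = Φ[(0.22 − 1.96 × 0.0791)/0.0771] = Φ(0.84) = 0.800

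The stated 76 per arm reproduces.

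**Step 3. Illustrate the effect of rescue.** Two assumptions that the documents do not supply:

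1. 50% and 72% are relapse-free rates.
2. A share r of each arm's failures is in sinus rhythm at the visit because of rescue.

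The observed rate in an arm is p + (1 − p)r, so the observed difference is 0.22 + 0.28 r_A − 0.50 r_D. With equal r this is 0.22(1 − r). Power uses the same test at 76 per arm.

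| r drug | r ablation | Observed rates | Difference (points) | Power |
|---|---|---|---|---|
| 0 | 0 | 50% vs 72% | 22.0 | 0.800 |
| 10% | 10% | 55% vs 74.8% | 19.8 | 0.729 |
| 20% | 20% | 60% vs 77.6% | 17.6 | 0.651 |
| 30% | 30% | 65% vs 80.4% | 15.4 | 0.569 |
| 40% | 40% | 70% vs 83.2% | 13.2 | 0.485 |
| 30% | 10% | 65% vs 74.8% | 9.8 | 0.259 |
| 10% | 30% | 55% vs 80.4% | 25.4 | not a valid gain |

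In the last row the observed difference exceeds the assumed true 22 points, so any extra power would come from bias.

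**The case against.** The strongest reply is that the first primary should not be read alone. Freedom from AF is also a primary endpoint and addresses maintenance. On its natural reading, a patient with documented AF who is then cardioverted is not free of AF. Rhythm at 1 year under a treatment strategy, paired with freedom from AF and with cardioversions reported separately, is a coherent set of endpoints. This stands in part: a reader might infer that a rescued patient is a success for the trial as a whole, and the documents do not support that. They support it for the first primary, and for the second only if unscheduled findings are left out.

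Three other stronger readings also go too far.

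- **That the plan freely permits cardioversion in follow-up.** It does not say so. It counts cardioversions as an outcome and, in the text available, sets no restriction. The SAP text, part of the Protocol and its flow-chart figure were not available for review. The Follow up section also says it agrees with a cited consensus statement. A scoring rule in any of these cannot be excluded.
- **That the Background shows late rescue to be routine.** The remark that "patients get early cardioversion, before they are spontaneously reverted to sinus rhythm" explains why paroxysmal and short-term persistent AF are hard to tell apart. It is not about rescue after randomization.
- **That the trial has lost a known amount of power.** Every r is assumed. If 50% and 72% describe the second primary, or already describe 1-year rhythm with rescue, the loss in the table does not follow.

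A fair objection also applies to any scoring rule that starts at month 3. The Drug arm section says that amiodarone, allowed only after a level 1 drug has failed, can be finally judged only 6 months after its initiation. A month-3 start could fail drug-arm patients before the Protocol regards their treatment as assessable.

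**Conclusion.** The concern holds for the first primary endpoint as worded: it measures rhythm at one visit after any rescue, while Hypothesis 1 is about "maintenance of sinus rhythm after 1 year". The second primary covers this only partly, because of the gap in recordings between months 6 and 12, the undefined set of measurements and the unstated relation between the two primaries.

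The size and direction of the effect in this trial are unknown. Under the two assumptions in the working, equal rescue of 10% to 40% of failures lowers power from 0.80 to between 0.729 and 0.485. Unequal rescue of 30% against 10% moves the difference to 9.8 or 25.4 points, depending on which arm is rescued more. These figures show sensitivity and are not estimates. The conclusion about the definition does not depend on them.

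**What to change.** Amend the endpoint definition, before outcome data are examined by arm, as follows.

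1. Electrical or pharmacological cardioversion for AF, or repeat ablation, after the blanking period counts as AF recurrence, and so as failure, for both primary endpoints and in both arms.
2. Record the date and type of each event. The secondary endpoint as written asks only for a number.
3. Define the measurements that count for freedom from AF, including whether unscheduled ECGs do.
4. State how the two primaries combine and to which one 50% and 72% apply.
5. Keep plain sinus rhythm at the 1-year visit as a supporting result.

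Two points need care in the wording. The start of scoring in the drug arm must be reconciled with the statement on when amiodarone's efficacy can be judged. Pharmacological cardioversion must be defined so that the drug changes allowed in the Drug arm section are not counted as failures. The text should also say how a first ablation after cross-over is scored, so that it and a repeat ablation are handled consistently.

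**Cost.** A few sentences, slightly more detailed event recording, and lower reported success rates in both arms. Patient care does not change. If 50% and 72% are confirmed as relapse-free rates, 76 per arm still gives power 0.80 under this definition.

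### Two primary endpoints stand unlinked, and the first, a single unconfirmed rhythm reading at 1 year, can count a patient with AF recorded on Holter as a success

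*Protocol*

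**What the plan says.** Protocol, ENDPOINTS, gives two primary endpoints as separate bullets: "Sinus rhythm at clinical visit at 1 year after the ablation, or with AAD" and "Freedom of AF with all measurements". It does not say whether one or both must be met, or which takes precedence.

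Protocol, HYPOTHESIS, item 1, expects cryoballoon ablation (CBA) to do better than drug therapy in keeping patients in sinus rhythm at 1 year.

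Protocol, INCLUSION/EXCLUSION CRITERIA, judges eligibility on past episodes. A patient needs two symptomatic episodes, each above a 30-second minimum, and must have had AF at some point in the preceding year. The long qualifying episode is worded as follows: "One episode cardioverted after more than 7 days or spontaneously terminated after more than 7 days". The introductory text adds: "If one episode is paroxysmal it should have been lasting minimal 30 sec". No criterion asks for AF at inclusion.

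Protocol, RATIONALE, supports the choice of population partly by saying that "the endpoints for persistent patients are much easier than for paroxysmal patients".

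Protocol, FOLLOW UP, schedules office ECGs at months 3, 6 and 12, a 24-hour Holter at month 3 (described as falling in the blanking period), a 48-hour Holter at month 6, and at month 12 "7 days Holter: with a clinical device".

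Protocol, SAMPLE SIZE, assumes 1-year success of 50% on drugs and 72% on CBA, and does not say which primary endpoint these rates describe.

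**The concern.** The first primary endpoint is a state on one day. Entry admits patients who are already in that state and whose AF can stop without treatment. A patient whose intermittent AF is unchanged can therefore be scored as a success, provided that he or she is in sinus rhythm on the day of the 1-year visit. The Holters that would show the recurrence are scheduled but are not part of this endpoint's definition.

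The argument that persistent AF is easy to score does not fully protect the endpoint. The criteria accept self-terminated long episodes and count a paroxysm as one of the two episodes. The BACKGROUND section itself says that paroxysmal and short-term persistent AF can hardly be told apart in practice.

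Two things are at stake. The two primaries can classify the same patient differently, and nothing says which result carries the trial's conclusion. The first may also have less power than planned, depending on what the 50% and 72% stand for.

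**Working it through.** **Step 1. Compare the two primaries on one patient.** Take a patient who entered in sinus rhythm, has AF on the month-6 48-hour Holter or the month-12 7-day Holter, and is in sinus rhythm at the month-12 visit.

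- First primary: success, because only visit-day rhythm counts.
- Second primary: failure, because AF was found on a measurement.
- Hypothesis 1: sinus rhythm was not maintained.

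**Step 2. Reproduce the planned sample size.** Inputs from SAMPLE SIZE: p1 = 0.50, p2 = 0.72, power 0.80, significance 0.05 (taken as two-sided, which is not stated). With the pooled-variance formula and no continuity correction:

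n = [1.960 × √(2 p̄(1−p̄)) + 0.842 × √(p1(1−p1) + p2(1−p2))]² / (p2−p1)², with p̄ = 0.61

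= [1.960 × √0.4758 + 0.842 × √0.4516]² / 0.0484 ≈ 76 per arm.

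This matches the plan. Power at 76 per arm is 0.800.

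**Step 3. Effect of a single reading.** Assume that 50% and 72% are true freedom-from-AF rates. Let m be the share of recurrent patients who are in sinus rhythm on the visit day, equal in both arms. Then:

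- drug arm success = 0.50 + 0.50 m
- CBA success = 0.72 + 0.28 m
- difference = 0.22 × (1 − m)

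The documents do not give m. To set a range, write m = q × (1 − b). Here q is the share of recurrences that are self-terminating and b is the fraction of time such patients spend in AF. Take b = 0.10 (about 36.5 days a year) and q = 0.10, 0.25 and 0.50. Both are assumptions.

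| q | m | Drug | CBA | Difference | Power, 76/arm | n/arm for 0.80 |
|---|---|---|---|---|---|---|
| 0 | 0 | 50.0% | 72.0% | 22.0 points | 0.80 | 76 |
| 0.10 | 0.09 | 54.5% | 74.5% | 20.0 points | 0.74 | 89 |
| 0.25 | 0.225 | 61.3% | 78.3% | 17.1 points | 0.63 | 113 |
| 0.50 | 0.45 | 72.5% | 84.6% | 12.1 points | 0.44 | 180 |

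The drug arm gains more, because it has more recurrent patients to misclassify (50% against 28%). With equal m, any m above 0 narrows the difference.

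**Step 4. The other reading of 50%/72%.** If these rates already describe visit-day sinus rhythm, the first primary keeps its planned power. SAMPLE SIZE then says nothing about the second primary. The text does not settle which reading applies.

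**The case against.** The strongest reply is that the second primary already does the work. A patient with AF on a scheduled Holter fails "Freedom of AF with all measurements". A reader might infer from the first bullet that the trial's primary assessment has no confirmation at all. The documents do not support that. What remains is that the two primaries are not linked, so a claim resting on visit-day rhythm alone is not excluded.

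A reader might also infer that the planned power of 0.8 is lost. That does not follow either. SAMPLE SIZE ties 50%/72% to neither endpoint, and m, q and b come from outside the documents. Every patient needs one long episode (more than 7 days, with an edit to 48 h also visible in the introductory text), and BACKGROUND says that patients are usually cardioverted early. Both argue against a large self-terminating share. A value of m near 0 is possible, and the loss would then be negligible.

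A third tempting reading is that the single reading manufactures a benefit for ablation. With an equal share in both arms it does the opposite: it pulls the difference towards zero. Starting in sinus rhythm is also no defect in itself, since the hypothesis is about keeping it and the comparison is with a concurrent randomised arm.

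It can further be said that a rule counting month-6 AF as failure is hard on drug-arm patients who move to amiodarone. INTERVENTIONS says that its final efficacy can be judged only 6 months after it is started, so any start after month 0 puts that point beyond month 6. The tension is real, but it is not new: the second primary, as worded, already counts month-6 AF.

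Finally, the SAP text and the flow chart were not available to check, so a fuller definition or a hierarchy there cannot be excluded.

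**Conclusion.** The point holds in a limited form. The protocol has two primary endpoints that can disagree on the same patient and no rule linking them. The first is an unconfirmed single reading that does not measure maintained sinus rhythm. This rests on the protocol's wording alone and needs no assumption.

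The size of any power loss is conditional. It requires that 50%/72% are freedom-from-AF rates and that some recurrent patients, in equal share by arm, are in sinus rhythm on the visit day. Under those assumptions, power on the first primary runs from 0.80 (no such patients) to about 0.44 (45% of them). The direction is towards no difference. The sample-size arithmetic itself is sound.

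This should be corrected, because the remedy is cheap and uses data already planned.

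**What to change.** In ENDPOINTS, name one primary endpoint: freedom from AF on the scheduled recordings after the blanking period, namely the month-6 ECG and 48-hour Holter and the month-12 ECG and 7-day Holter. This should sharpen and replace the existing second bullet, because adding a confirmation rule to the first would leave two nearly identical primaries. Move sinus rhythm at the 1-year visit to the secondary endpoints. In SAMPLE SIZE, state that 50% and 72% refer to the AF-free definition, after checking that the sources behind them used a comparable one.

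The cost is wording only; no visit, device or recording is added. There are three consequences to accept or settle:

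- Success rates in both arms will be lower than with a visit-day reading.
- Patients without the month-12 Holter cannot be confirmed, so a handling rule must be stated in advance.
- AF at month 6 counts as failure. This must be reconciled with the INTERVENTIONS statement on when amiodarone efficacy can be judged.

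### The second primary endpoint names only AF, so a patient in atrial flutter or atrial tachycardia can pass it while failing the first primary endpoint, and can pass both if the rhythm appears only on a Holter.

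*Protocol*

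**What the plan says.** The Protocol, Endpoints, lists two primary endpoints: "Sinus rhythm at clinical visit at 1 year after the ablation, or with AAD" and "Freedom of AF with all measurements". The first fails on any rhythm other than sinus. The second names AF alone, and it is the only primary endpoint that can draw on the Holters (Protocol, Follow up).

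The Protocol, Hypothesis, gives as its aim the "endpoint maintenance of sinus rhythm after 1 year and an improved QOL in the ablation group".

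Atrial flutter appears once, as an exclusion criterion: "Pure (typical) atrial flutter as documented on one occasion". Atrial tachycardia is not mentioned. A minimum episode length appears only at entry: "history of 2 symptomatic AF episodes more than 30 sec".

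The Protocol, Sample size, states "The maximal expected 1 year success on AAD is 50"% and "minimal expected success of CBA is 72"%. It does not say which primary endpoint, or which definition of success, these rates describe.

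**The concern.** The two primary endpoints use different failure events. One asks whether the patient is in sinus rhythm; the other asks whether AF was seen. Sustained flutter or atrial tachycardia separates the two: it is not sinus rhythm, and on the literal wording it is not AF.

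Two things are at stake. First, one patient can be a failure on one primary endpoint and a success on the other, with no rule for reading the disagreement. Second, the only primary endpoint that uses the longer recordings may overlook an outcome that contradicts the hypothesis. If such cases are not equally frequent in an arm treated by a procedure and an arm treated with drugs, the treatment difference on that endpoint may be distorted.

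**Working it through.** **Classification on the literal wording**

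| Patient (no AF on any recording) | Endpoint 1: sinus rhythm at 1 year | Endpoint 2: AF-free | Sinus rhythm maintained? |
|---|---|---|---|
| Flutter or atrial tachycardia at the 12-month visit | Fail | Pass | No |
| Flutter or atrial tachycardia only on the month-6 or month-12 Holter, sinus rhythm at the visit | Pass | Pass | No |

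**The plan's own figure.** Inputs from Protocol, Sample size: 50% against 72%, power 0.80, significance 0.05, allocation 1:1. The sidedness is not stated; a two-sided test reproduces the figure. With pooled variance and no continuity correction, the average rate is 0.61 and

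n = [1.960 × √(2 × 0.61 × 0.39) + 0.842 × √(0.50 × 0.50 + 0.72 × 0.28)]² / 0.22² = (1.352 + 0.566)² / 0.0484 ≈ 76 per arm.

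This matches the protocol. The total of 167 is 152 × 1.10.

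**What the definition could change.** The documents give no flutter or tachycardia rates, so every share below is an assumption. The answer also depends on what 50% and 72% mean, so both readings are shown.

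*Reading A: the planned rates already count flutter and tachycardia as failures.* Ablation failures are 0.28 × 76 = 21.3. Let s be the share of failures that are flutter or tachycardia only. AF-only scoring then reads 0.72 + 0.28s for ablation and, where such cases occur on drugs, 0.50 + 0.50s for the drug arm. The true difference is 22 points.

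| s | Ablation patients reclassified | Ablation success reads | Difference, cases in ablation arm only | Difference, same s in both arms: 22 × (1 − s) | Difference, cases in drug arm only: 22 − 50s |
|---|---|---|---|---|---|
| 10% | 2.1 | 74.8% | 24.8 | 19.8 | 17.0 |
| 20% | 4.3 | 77.6% | 27.6 | 17.6 | 12.0 |
| 30% | 6.4 | 80.4% | 30.4 | 15.4 | 7.0 |

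*Reading B: the planned rates are AF-only.* Some of the planned successes then have flutter or tachycardia and become failures once those rhythms count. With p1 and p2 the reduced success rates and p̄ their average,

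power = Φ{[√76 × (p2 − p1) − 1.960 × √(2p̄(1 − p̄))] / √(p1(1 − p1) + p2(1 − p2))}.

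For 5% in the ablation arm only, p2 = 0.67 and p1 = 0.50, so power = Φ[(1.482 − 1.366) / 0.686] = Φ(0.169) = 0.57.

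| Share of the arm | Ablation arm only: power (n per arm for 0.80) | Both arms equally | Drug arm only |
|---|---|---|---|
| 2% | 0.72 (93) | 0.79 (78) | 0.86 (65) |
| 5% | 0.57 (131) | 0.79 (79) | 0.93 (52) |
| 10% | 0.32 (268) | 0.78 (80) | 0.98 (37) |

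Under either reading the direction depends on which arm has the cases. Under Reading B, equal rates in both arms hardly matter.

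**The case against.** The strongest reply is that AF may have been shorthand for any atrial tachyarrhythmia, with the recurrence definition placed elsewhere. The SAP text, part of the protocol and the flow charts were not available to this review. The Follow up section also says that it "Is in agreement with proposal in ref 23", a consensus statement whose title includes definitions and endpoints. This limits confidence, because an absence cannot be proved from incomplete text. It does not settle the matter: the reference is attached to follow-up, and the available text takes no endpoint definition from it.

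Other parts of the reply also stand:

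- A reader might infer from the exclusion of flutter at entry that sites would code flutter in follow-up as something other than AF. The criterion covers only pure, typical flutter and says nothing about coding recurrences. It shows that the protocol can tell the rhythms apart, no more.
- A reader might infer that the comparison is biased in favour of ablation. The documents contain no rates and no statement of how often either treatment leads to these rhythms, so neither the existence nor the direction of bias is shown.
- A reader might take 75–80% as the expected distortion. That holds only under Reading A. The Protocol, Background, quotes 69–77% freedom from AF after cryoballoon ablation. That range contains 72% and shares a reference with the sample-size section, so Reading B is at least as plausible.
- A reader might say such patients are counted as cured. A patient in flutter at month 12 still fails the first primary endpoint, and any cardioversion enters a secondary endpoint.
- The two endpoints also differ by design, one being a single visit and the other all measurements. AF at month 6 with sinus rhythm at month 12 would separate them under any definition. Only the disagreement caused by flutter or tachycardia is at issue here.

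**Conclusion.** The point holds as a defect in the wording of a primary endpoint. Followed literally, the rule scores flutter and atrial tachycardia as success on the second primary endpoint. That conflicts with the first endpoint when the rhythm is present at the 12-month visit, and with the hypothesis in either case.

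The effect on the trial's result is unknown. On assumed shares confined to the ablation arm, it ranges from an apparent success of 75–80% instead of 72% (Reading A) to power of 0.72, 0.57 or 0.32 once 2%, 5% or 10% of the arm is reclassified (Reading B). Cases confined to the drug arm act in the opposite direction. The supportable statement is that the comparison may be biased if frequencies differ between arms.

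The change is worth making because it is cheap. Confidence is medium, since a definition in the text not available here cannot be excluded.

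**What to change.** Define the second primary endpoint as freedom from AF, atrial flutter and atrial tachycardia lasting at least 30 seconds, the duration already used at entry. Say how an office ECG shorter than that is scored. Report freedom from AF alone as a secondary endpoint. In the sample-size section, state which endpoint and which definition of success the 50% and 72% describe. If the SAP already contains such a definition, repeat it in the protocol's endpoint list.

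The cost is one line in the endpoint definition, one sentence in the sample-size section and a rhythm-type field for recurrences in the CRF. No new recordings are needed. The downside is somewhat lower success rates. If 72% is an AF-only figure, the stated power may also need restating, with the second table above as a guide to the range.
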